| Local Tolerability (7)                |   | X |       | X | X |        | X      |
| Dispense subject diary                |   | X |       | X |   |        |        |
| Collect and review subject diary      |   |   |       | X | X |        | X      |
| Safety phone call (9)                 |   |   | x (9) |   |   | x (10) |        |

- (1) Early termination visit should – if possible - be conducted 28±3 days after last IMP administration.
- (2) Systolic/diastolic blood pressure, pulse rate, body temperature
- (3) Conditions/symptoms noted prior to randomization should not be reported as AE, but should be reported as medical history
- (4) Medications administered up to 30 days prior to screening until end of study participation should be documented
- (5) The clinical laboratory comprises: Hematology (hemoglobin, hematocrit, erythrocyte count, differential white blood count, platelets), Chemistry (creatinine, potassium, sodium, calcium, AST, ALT, alkaline phosphatase, bilirubin), Coagulation (prothrombin time (PT), activated partial thromboplastin time (aPTT), fibrinogen), Urinalysis (standard urine test stick for determining pH-value, glucose, protein, bilirubin, urobilinogen, red blood cells, white blood cells, nitrite, ketone and specific gravity), Virology (only at screening; HBs-Ag, anti-HBc-Ab, anti-HCV-Ab, HIV 1/2 Ab/HIV-1 Antigens if not done within 30 days before screening)
- (6) To be performed if necessary, according to findings in symptom-directed physical examination
- (7) To be performed 1 hour after each IMP administration and additionally at the subsequent visit (prior to IMP administration, if applicable)
- (8) Participants should be interviewed regarding potential AEs since the last study visit. If indicated, participants should be called in for an unscheduled visit.
- (9) The post dose safety call follows up should be conducted 7±1 days (one week) after the first vaccination.
- (10) The post treatment safety call follows up should be conducted 182 days (6 months) after the first study treatment also in case of an early termination.
- (11) The amount of blood sample taken during the early termination (ET) visit depends on the time point of the visit. If the ET-visit replaces the primary endpoint visit on day 56±3, 48 to 60 mL blood should be taken; otherwise 24 to 48 mL are enough.
- (12) Urine for pregnancy test should be taken before vaccination

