***Please note:***

*As this is a first in humans' study, the site should initially enroll a group of six participants and then pause with enrollment until these participants completed their Post Dose Safety Follow Up one week after the first vaccination. If no events as defined in section 8.9.1 "Safety Stopping Rule" are identified, the site should resume enrolling participants. If such events were identified, the investigators and the sponsor need to assess the risk of continuing the study and based on this assessment to decide if or if not, the study should be continued.*

The 48 participants will be distributed between the 4 groups using a randomisation ratio of 14 : 14 : 12 : 8 = A : B : C : D, with an adequate representation of high dose, low dose and placebo subjects (2 : 2 : 0 : 2 = A : B : C : D) within the first 6 subjects to allow for the safety evaluation after the first vaccination.

A subject will be considered enrolled once the first IMP administration has been performed according to randomisation.

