### **8.5.2 Post Dose Safety Follow-up (day 7 $\pm$ 1 days)**

The investigator will ensure phone contact with the participants one week after first vaccination was performed and ask about any new concomitant medications or AEs occurred since the last visit. If deemed necessary, the investigator may ask participants to come to study site for an unscheduled visit to assess severity of the AEs.

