### Individual Participants Stopping Rules

The following are specific criteria for discontinuing individual participants from further vaccination, but not from completing scheduled follow-up assessments, unless the participant is explicitly withdrawn from the study:

- Participants who develop serious adverse reaction (SAR) at the discretion of the investigator
- Participants who develop a potentially life-threatening (grade 4) solicited systemic adverse reaction that occurs without alternative etiology within 7 days after the study vaccination
- Participants who develop a medical condition for which continued participation, in the opinion of the investigator, would pose a risk to the subject or would be likely to confound interpretation of the results
- Participants who become pregnant during the treatment phase of the study
- Participants who experience anaphylaxis within 24 hours or generalised urticaria within 72 hours after administration of the study vaccine

If any of these occur, appropriate measures to treat the subject will be taken and the sponsor or the sponsor designee will be notified immediately.

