### Entire Study Stopping Rules

The study will be stopped (no new enrolments and no additional vaccine administered) pending a safety review by the investigator and the sponsor, if any of the following occurs:

- One or more participants experience a serious adverse reaction (SAR), based on the current reference safety information (Investigator's Brochure)
- One or more participants' deaths assessed by the investigator, safety manager or sponsor as related to investigational product
- One or more participants develop laryngospasm, bronchospasm or anaphylaxis within 24 hours of vaccine administration
- Two or more participants develop injection-site ulceration, abscess or necrosis
- Two or more participants experience generalised urticaria within 72 hours after administration of study product

Upon completion of this review, the sponsor will determine if study enrolment or treatment should be discontinued, or if study enrolment and treatment may continue according to the protocol.

Irrespective of the stopping rules the study may be temporarily suspended or prematurely terminated at any time if there is sufficient reasonable cause, and if agreed to by both the investigator and the sponsor as being in the best interests of participants and justified on either medical or ethical grounds. In terminating the study, the sponsor, the CRO, and the investigator will ensure that adequate consideration is given to the protection of the participants' interests.

Whenever the study is stopped the competent authorities and ethical committees will be informed.

In case the entire study has to be discontinued prematurely, all concerned participants should be asked to perform an early termination visit.

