## 11.7 Subject Diary

The participants will be instructed to complete a diary for 7 days after each vaccination to document local and systemic tolerability as well as body temperature.

Solicited local and solicited systemic AEs will be assessed by the participants themselves by checking for presence of the listed symptoms and measuring the size of the affected area where appropriate (a template will be provided for local reaction grading, as shown in Appendix 1). The diary will also provide space for recording unsolicited AEs and concomitant medication.

Recording should be done approximately at the same time each day, starting on the day of vaccination. The first entry should be made 6 hours  $\pm 1$ h after vaccination at Visit 1 and Visit 2.

The participants' diaries will be collected and verified for completeness by the investigator at Visit 2 and Visit 3. Any AE recorded in the subject diaries will be entered in the eCRF by the investigator or authorised delegates. The investigator will re-evaluate the severity of the reported local and systemic AEs according to the below Tables 5 and 6.

Diary solicited systemic AEs include nausea, vomiting, headache, and fatigue, also to be documented in the eCRF.

In addition, body temperature will be recorded daily for 7 days and fever will be graded by the investigator according to the FDA Guidance for Industry. For details see below Table 6. Table 5. Grading of local reactions

| Local reaction to injectable product | Mild (grade 1) | Moderate (grade 2) | Severe (grade 3) | Potentially life threatening (grade 4) |
|--------------------------------------|----------------|--------------------|------------------|--|
|--------------------------------------|----------------|--------------------|------------------|--|

|   |   |  |  |  |
|---|---|--|--|--|
| Pain                             | Does not interfere with activity            | Interfere with activity or repeated use of non-narcotic pain reliever  | Prevents daily activity or repeated use of non-narcotic pain reliever                    | Emergency room (ER) visit or hospitalisation |
| Tenderness                       | Mild pain to touch                          | Pain with movement   | Significant pain at rest   | ER visit or hospitalisation                  |
| Erythema/ Redness    | ≤ 5 cm                                      | 5.1–10 cm  | > 10 cm  | Necrosis or exfoliate dermatitis             |

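### The six-participant enrolment pause can end without diary temperatures being seen and, if Section 8.2 means all of Section 8.9.1, up to a day before a 7-day criterion closes

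*Combined protocol and SAP*

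**What the plan says.** Protocol Section 8.2 has the site enrol six participants (2 : 2 : 0 : 2 across A to D) and then "pause with enrollment until these participants completed their Post Dose Safety Follow Up one week after the first vaccination". The release condition begins "If no events as defined in section 8.9.1" and cites that section without naming a part of it. If such an event is found, the investigators and sponsor assess the risk and decide whether to continue.

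Section 8.5.2 describes the follow-up as "phone contact with the participants one week after first vaccination was performed and ask about any new concomitant medications or AEs occurred", and allows the investigator to call a participant in for an unscheduled visit. Table 2 footnote 9, repeated in SAP Section 1.5, sets the timing: "The post dose safety call follows up should be conducted 7±1 days (one week) after the first vaccination".

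Section 8.9.1 says it has rules at two levels.
- The individual list stops further vaccination of one participant. It includes a grade 4 "solicited systemic adverse reaction that occurs without alternative etiology within 7 days after the study vaccination".
- The entire-study list stops the trial ("no new enrolments and no additional vaccine administered"). Its time-limited entries run to 24 h, or to 72 h at the longest: "Two or more participants experience generalised urticaria within 72 hours after administration of study product".

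Participants record temperature and adverse events in a diary for 7 days, starting 6 h after injection (Sections 8.5.1 and 11.7). Section 11.7 adds: "Recording should be done approximately at the same time each day, starting on the day of vaccination". Diaries are collected and checked at Visits 2 and 3. Both procedures tables mark diary review only at V2, V3 and early termination. At the phone follow-up they mark adverse events, medication and the call itself.

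**The concern.** This is the only planned enrolment pause in a first-in-human trial. The phone call is also the only scheduled contact between discharge on Day 0 and Visit 2. Two features of the release decision look looser than they need to be.

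First, the call may be made before the longest time window in the cited section has run out, if the individual list counts. Second, the data collected specifically to capture reactogenicity over that week need not be looked at.

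Fever is where the second feature matters most. In Table 6 the other grade 4 rows mean an emergency visit or hospitalisation, which a participant would be likely to report and which could fall under the serious adverse reaction rule. Fever above 40.0 °C is grade 4 on the thermometer reading alone. If isolated and non-serious, it appears on no study-level list.

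**Working it through.** No sample size, power or error rate is involved; the check is of dates and hours.

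**1. The plan's own count.** 2 + 2 + 0 + 2 = 6, which agrees with Section 8.2. Four of the six (A and B) receive vaccine.

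**2. Call window.** 7 ± 1 days gives Day 6 to Day 8.

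**3. Timing if all of Section 8.9.1 applies.** In whole days, 7 − 6 = 1 day short for a Day 6 call, and 0 for Day 7 or Day 8. In hours, assume the call is at the clock hour of the injection:
- the window is 7 × 24 = 168 h and the call is at 6 × 24 = 144 h, so 168 − 144 = 24 h remain;
- a participant dosed x h before the last one is then at 144 + x h, so the window is still open at release only if x < 24. This affects the last-dosed participant and any dosed less than a day earlier.

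**4. Timing if only the entire-study list applies.** At 144 h the 72 h criterion closed 144 − 72 = 72 h earlier, and the 24 h criterion 144 − 24 = 120 h earlier. The timing gap is 0.

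**5. Diary entries made by then.** Daily entries from 6 h fall at 6, 30, 54, 78, 102, 126 and 150 h, ignoring the ±1 h tolerance on the first. Six of seven precede a 144 h call; the last is 150 − 144 = 6 h away. A Day 6 call at 150 h or later has all seven entries available but leaves up to 168 − 150 = 18 h of the 7-day window.

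**6. When the diary must be seen.** Visit 2 is at 28 ± 3, so Day 25 to Day 31. The shortest lag after the call is 25 − 8 = 17 days, the longest 31 − 6 = 25, and the nominal one 28 − 7 = 21. This holds on either reading of Section 8.2.

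**7. The two gaps are separate.** A call at 168 h or later brings the gap in step 3 to 0. It does nothing for step 6, because a later call does not by itself put the diary in front of anyone.

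**The case against.** The strongest reply is that Section 8.2 governs enrolment, and only the entire-study list speaks of enrolment. The individual list concerns one participant's further doses and includes pregnancy, an odd reason to hold a dose-safety gate. The revision index for Version 1.8 also records the ethics committee's request in terms of serious events. On this reading there is no timing gap, and no release criterion uses temperature.

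That reading is possible but not compelled. Section 8.2 cites Section 8.9.1 without restriction, and Section 8.9.1 opens by naming both levels. Entire-study events already stop enrolment on their own terms, so a gate limited to them would add little. Counting a pregnancy would lead only to the risk assessment in Section 8.2, not to an automatic stop.

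Several other points stand and limit the weight:
- A diary reading can change the release decision by rule only if the individual list counts. Otherwise a high fever informs the decision without holding the gate.
- Even then, fever must count as a solicited systemic reaction, and one without another cause. Table 6 lists fever, but Section 11.7 names nausea, vomiting, headache and fatigue and adds temperature separately.
- Participants are asked directly about adverse events, may be called in, and remain under the stopping rules after release. Serious events are reportable within 24 hours (Section 10.3).
- The protocol works in days, so the hour figures depend on the assumed call time.

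A reader might infer that a grade 4 reaction among the six would go unnoticed, or that the gate is bound to open early. The documents support neither: Day 6 is permitted, not prescribed, and the diary gap is a missing requirement, not a bar to seeing the data. Nor can a chance of missing an event be given, since there is no event rate for this product.

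**Conclusion.** The point holds as a small one. If Section 8.2 means the whole of Section 8.9.1, a Day 6 call can release enrolment up to one day before the 7-day criterion closes for the last-dosed participant(s). If it means only the entire-study list, that gap is nil. On both readings the plan allows release without any diary temperature having been seen.

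The conclusion rests on the text of Sections 8.2, 8.5.2, 8.9.1 and 11.7 and of the two procedures tables. The 24 h figure also assumes a call at the clock hour of the injection. The consequence is limited mainly to an isolated, non-serious fever above 40.0 °C that the participant does not mention when asked. The change is a cheap improvement in safety wording, not a correction on which the trial's conclusions depend.

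**What to change.** In Sections 8.2 and 8.5.2, in Table 2 footnote 9, and in the copy in SAP Section 1.5, state for the six initial participants only:
- the call is made no earlier than 168 h after vaccination and no later than Day 8;
- diary entries and daily temperatures are read out and recorded at that call, before enrolment resumes.

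In Section 8.2, also state that both lists in Section 8.9.1 govern release. The other 48 − 6 = 42 participants keep 7 ± 1 days.

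The earliest restart moves from Day 6 to late Day 7 or Day 8, that is 7 − 6 = 1 to 8 − 6 = 2 days later; the latest call stays at Day 8. No visit, call or sample is added. The wording needs an approved amendment under Section 16.1 and could travel with another one.

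The pause may already be over: planned first subject in was August 2019, and the Version 2.1 entry of September 2020 describes antibody testing in the past tense. If so, document when the six calls were made and whether temperatures were seen, and carry the wording into any successor protocol.

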## 7. PARTICIPANT IDENTIFICATION

### 7.1 Trial Participants

Healthy male and female volunteers will be screened for inclusion and exclusion criteria and randomised to one of 4 treatment groups in case of eligibility.

Forty-eight participants will be enrolled if all the following inclusion criteria and none of the following exclusion criteria apply:

### 7.2 Inclusion Criteria

1. Signed informed consent obtained before any trial-related activities
2. Healthy men or women aged 18 to 55 years on the day of consenting
3. Ability to comprehend the full nature and purpose of the study, including possible risks and side effects; ability to cooperate with the investigator and to comply with the requirements of the entire study
4. All female participants must have a negative urine pregnancy-test at screening
5. Willingness not to become pregnant or to father a child during the entire study period by practicing reliable methods of contraception as specified in protocol section 8.11.4
6. Availability during the duration of the trial
7. Normal findings in medical history and physical examination or the investigator considers all abnormalities to be clinically irrelevant
8. Normal laboratory values or the investigator considers all abnormalities to be clinically irrelevant (unless otherwise specified in exclusion criteria)

### 7.3 Exclusion Criteria

The subject may not be enrolled in the study if any of the following applies:

1. Participation in another clinical study (including exposure to an investigational medicinal product or device) within one month before the screening visit or planned concurrent participation in another clinical study before completion of the treatment period (day 56)
2. History of immunodeficiency, known human immunodeficiency virus (HIV) infection or current hepatitis B/C infection
3. Strong anamnestic evidence for or confirmed history of or current infection with Zika- or Dengue-virus
4. History of drug addiction including alcohol dependence within the last 2 years

5. Inability or unwillingness to avoid intake of more than around 20g alcohol per day during 48 hours after each vaccination (equals roughly 0.5 L beer or 0.25 L of wine)
6. Vaccination within 4 weeks prior to first vaccination or planning to receive any non-study vaccine until end of treatment period (day 56)
7. Prior receipt of any Zika or Chikungunya vaccine
8. History of moderate or severe arthritis or arthralgia within the past 3 months prior to Screening Visit
9. Recent infection within 1 week prior to Screening Visit (possibility of deferral)
10. Blood donations including plasma donations, 90 days prior to Screening Visit and anticipated blood, plasma, tissue, sperm, or organ donation, throughout the study until end of treatment period (day 56)
11. Clinically relevant history of renal, hepatic, gastrointestinal, cardiovascular, respiratory, skin, haematological, endocrine, inflammatory, autoimmune, or neurological diseases or clinically relevant abnormal laboratory values, that in the opinion of the investigator may interfere with the aim of the study
12. History of neoplastic disease (excluding non-melanoma skin cancer that was successfully treated) within the past 5 years or a history of any haematological malignancy
13. Behavioural, cognitive, or psychiatric condition that in the opinion of the investigator affects the ability of the participant to understand and cooperate with the study protocol
14. History of severe adverse reactions to vaccine administration, including anaphylaxis and related symptoms, such as urticaria, respiratory difficulty, angioedema and abdominal pain to vaccines, or history of allergic reaction likely to be exacerbated by any component of the vaccine
15. History of anaphylaxis to drugs or other allergic reactions, which the investigator considers compromising the safety of the volunteer
16. Abnormal laboratory values which, at the discretion of the investigator should lead to the exclusion of the subject
17. Use of medication during 2 weeks before the first vaccination and throughout the study, which the investigator considers affecting the validity of the study, except hormonal contraception or hormonal replacement therapy in female participants. (Prior to taking any medication within 72 h before study vaccination, the subject should consult the investigator)
18. Use of immunosuppressive drugs like corticosteroids (excluding topical preparations) within 30 days prior to first IMP administration, or anticipated use until completion of the end of treatment visit Receipt of blood products or immunoglobulins within 120 days prior to the Screening Visit or anticipated receipt of any blood product or immunoglobulin before completion of the treatment period (day 56)

19. Pregnancy (positive pregnancy test at screening or during the treatment period) or lactation at screening, or planning to become pregnant during the treatment period
20. Unreliable contraception methods (for details please refer to protocol section 8.11.4)
21. Persons in a direct relationship with the sponsor, an investigator or other study team members. Direct dependent relationships include close relatives (i.e. children, parents, partner/spouse, siblings) as well as employees of the study site or the sponsor

## 8. TRIAL PROCEDURES

### 8.1 Informed Consent (AMG § 38)

In obtaining and documenting informed consent, the investigator must comply with the applicable regulatory requirement(s) and adhere to ICH guideline for GCP, the requirements in the Declaration of Helsinki and the EU directive 2005/28/EC.

Before any trial specific procedures are performed participants will be informed about the exact nature of the trial, what it will involve for the participant, all procedures as determined by the clinical protocol, the known side effects and any risks involved in taking part. It will be clearly stated that the subject is free to withdraw from the trial at any time for any reason without prejudice to future care, without affecting their legal rights and with no obligation to give the reason for withdrawal.

The participant will be allowed as much time as needed to consider the information, and the opportunity to question the investigator or other independent parties to decide whether they will participate in the trial.

Written informed consent will then be obtained by means of participant's dated signature and dated signature of the qualified and experienced person who presented and obtained the informed consent. A copy of the signed informed consent will be provided to the subject and the original signed form will be retained at the site.

If information becomes available that may be relevant to the subject's willingness to continue participating in the trial, the investigator must inform the subject in a timely manner, and a revised written informed consent must be obtained.

